#### 9.1.2.1 Visit B1 (Day 1)

Day 1 is regarded as the first day of IMP dosing. The following data collected at the 'End of Treatment' visit of the blinded phase will also be considered as Visit B1 data: vital signs, physical examination (including height and body weight), details of menstruation (for females), Tanner Staging (patients aged 10–17 [inclusive]), ECG, clinical laboratory samples (blood and urine for hematology, biochemistry, urinalysis, determination of serum IGF-1 levels [patients less than 18 years of age], and pregnancy tests [if appropriate]), IVRS and paper diary information from the blinded phase (including information regarding seizures, AEs, usage of rescue medication, concomitant AEDs, IMP dosing), epilepsy-related hospitalizations, AEs, concomitant medications and/or changes to medication, QOLCE/QOLIE-31-P, PGIC, SGIC/CGIC, SGIC-SD/CGIC-SD, Wechsler Tests, CBCL/ABCL, SCQ and the Vineland-II. Suicidality will be assessed in accordance with Section 9.2.12.8.

Patients will take their final dose of the blinded phase IMP in the morning of Visit B1, followed by collection of the blinded phase 'End of Treatment' assessments. Patients will be instructed to begin the Blinded Open-label transition, taking their first dose of Blinded Transition OLE IMP in the evening of Visit B1 (Day 1).

Patients or their caregivers will receive sufficient IMP for two weeks' home dosing together with a blinded transition phase. If an unacceptable AE develops at any time during transition, dosing should initially be suspended or amended, at the investigator's discretion, until the event has resolved or is well tolerated.

Patients or their caregivers will be given a paper diary to record information regarding AEs, IMP, usage of rescue medication, concomitant AEDs and IMP dosing. In addition, patients/caregivers will be instructed to complete a weekly seizure reporting diary until the Follow-up visit using the IVRS.

The investigator should review the laboratory results as soon as these become available. If the results raise any safety concerns, the investigator should consider whether it will be appropriate for the patient to continue to participate in the extension study, or if the patient should be withdrawn.

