#### 9.1.2.10 Visit B10 (Day 365, End of Treatment/Withdrawal Visit)

This visit will occur 364 days after Visit B1or following early withdrawal from the study. A visit window of  $\pm 7$  days from the scheduled visit date is permitted, but it is preferred that the visit is performed on the scheduled visit day where possible. The following assessments will be made at the 'End of Treatment'/Withdrawal visit: vital signs, physical examination (including height and body weight), details of menstruation (for females), Tanner Staging (patients aged 10-17 [inclusive]), ECG, clinical laboratory samples (blood and urine for hematology, biochemistry, urinalysis, determination of serum IGF-1 levels [patients less than 18 years of age] and pregnancy tests if appropriate [using both a serum sample and a urine dipstick]), IVRS and paper diary information (including information regarding seizures, AEs, usage of rescue medication, concomitant AEDs, IMP dosing), epilepsy-related hospitalizations, concomitant medications and/or changes to medication, AEs, OOLCE/OOLIE-31-P, SGIC/CGIC, PGIC, SGIC-SD/CGIC-SD, Wechsler Tests, CBCL/ABCL, SCQ and the Vineland-II. Suicidality will be assessed in accordance with Section 9.2.12.8. Provided that the risk/benefit outcome is favorable in the investigator's opinion, a blood sample will be taken for analysis of plasma concentrations of concomitant AEDs. The investigator must assess adherence to the dosing regimen.

All IMP (used and unused) will be collected and a check of the returned IMP against usage should be made. For patients who withdraw early, the IVRS will be contacted to confirm withdrawal from the study. For patients who immediately continue to use GWP42003-P following the 'End of Treatment' visit outside of the GWEP1521 study, the IVRS will be contacted to confirm the patient's completion of this study and the paper diaries will be collected.

For patients who do not immediately continue to use GWP42003-P following the 'End of Treatment' visit outside of the GWEP1521 study, IMP will be tapered at home (10% per day for 10 days). Additional IMP will be dispensed, if required, and instructions for tapering the dose will be provided. Patients who withdraw early should also begin the taper period following the Withdrawal visit (unless continued dosing is not possible due to an AE). Information will continue to be recorded in the paper diary during the taper period.

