#### 9.2.11 Patient Diary

A diary will be completed daily throughout the study. Patients or their caregivers will be instructed on how to complete the diary and will be asked to record information daily. The number and type of seizures and the severity of focal seizures as well as information on AEs, concomitant AEDs and rescue medication will be collected each day from baseline (Visit 2). Information on IMP intake will also be recorded each day from randomization (Visit 3) until completion of dosing or withdrawal (Visit 10/Withdrawal visit).

Seizure information, including the number and seizure subtype, as well as the severity of focal seizures and the number of episodes of *status epilepticus* will be collected through an IVRS telephone diary completed daily throughout the blinded phase of the study by the patient or their caregiver. This IVRS telephone diary will be completed on a weekly basis during the OLE. The patient or their caregiver will also complete a paper diary daily to record AEs, concomitant AEDs, IMP intake and rescue medication throughout the study.

The following seizure subtypes will be collected daily in the IVRS telephone diary:

- Focal motor seizures without impairment of consciousness or awareness#
- Focal seizures with impairment of consciousness or awareness#
- Focal seizures evolving to bilateral generalized convulsive seizures#
- Generalized seizures:
  - Tonic–clonic#
  - Tonic#
  - Clonic#
  - Atonic#
- 'Other' seizures:
  - Absence seizures\*\*
  - Myoclonic seizures\*\*

- Focal sensory seizures\*\*
- Infantile/epileptic spasms\*\*
- Episodes of status epilepticus

# To be included in primary seizure endpoint.

\*\* To be included in composite 'other' seizure count.

For the purposes of calculating the composite seizure score, the severity of focal seizures will be assessed according to the following criteria:

- Type 1 Focal motor seizures without impairment of consciousness or awareness.
- Type 2 Focal seizures with impairment of consciousness or awareness.
- Type 3 Focal seizures evolving to bilateral convulsive seizures.

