Where X corresponds to the treatment period estimate, or GWP42003-P ratio, and Y corresponds to the baseline period estimate, or placebo arm ratio.

Primary efficacy analysis will be performed using the ITT analysis set.

TSC-associated seizure frequency (28-day average) and percentage change in seizure frequency will also be presented using summary statistics. Percentage change from baseline in TSC-associated seizure frequency will be calculated as:

$$((\text{Frequency during the treatment period} - \text{Frequency during baseline}) \div \text{Frequency during baseline}) \times 100$$

The frequency during each period will be based on 28 day averages and calculated as:

$$(\text{Number of seizures in the period} \div \text{Number of reported days in IVRS in the period}) \times 28$$

For the TSC-associated seizure endpoints only, if patients are randomized with no TSC-associated seizures during the baseline period then the percentage change from baseline will be calculated as:

$$(\text{Frequency during the treatment period} + 1) \times 100$$

Open-label Extension:

The primary endpoint for the OLE is the safety of GWP42003-P, evaluated by assessing the incidence, type and severity of AEs. Data will be presented as per Section 5.6.2.

However, percentage change from baseline in TSC-associated seizure frequency is considered a key secondary endpoint for the OLE.

In the OLE, seizures are recorded on a weekly basis rather than daily. Caregivers/patients are expected to call the IVRS system to record the number of seizure subtypes experienced every 7 days during the OLE. TSC-associated seizure frequency per 28 days will be calculated for each of the periods described in Section 5.5.1. All calls that take place during the period in question will contribute to the calculation of the average number of seizures per day in that period only.

The average number of seizures per day in the period will be calculated as the average of:

$$\text{Number of seizures reported} \div \text{Number of days since last IVRS call}$$

The number of days since the last call will be calculated as follows, and is dependent on whether the call took place <7 , 7 or >7 days after the previous call (or after the date of OLE Day 1 in the case of the first call in the first period):

- If the call takes place exactly 7 days after the previous call, then the number of days since the last call will be 7.

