- If the call takes place <7 days after the previous call, then the number of days since the last call will be calculated as:
$$(\text{Date of current call} - \text{date of previous call}) + 1$$
- If the call takes place >7 days after the previous call, then the number of days since the last call will be 7.

Summary statistics will be presented for raw seizure frequencies and percentage change from baseline (from the blinded phase).

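### The OLE seizure-rate rule divides early IVRS calls by the gap plus one day but 7-day calls by the gap itself, and no stated recall window makes the early divisor right

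*SAP*

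**What the plan says.** In the Open-label Extension part of SAP 5.5.2, each call's seizure count is divided by a number of days since the last call. The period rate follows from these per-call rates: "The average number of seizures per day in the period will be calculated as the average of" those ratios.

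The day count has three branches:

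- On time: "If the call takes place exactly 7 days after the previous call, then the number of days since the last call will be 7".
- Early: for a call fewer than 7 "days after the previous call, then the number of days since the last call will be calculated as" current date minus previous date, plus 1.
- Late: for a call more than 7 "days after the previous call, then the number of days since the last call will be 7".

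The first call is measured from OLE Day 1.

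The blinded-phase frequency, which supplies the baseline for OLE percentage change, is built differently. SAP 5.5.2 says: "The frequency during each period will be based on 28 day averages and calculated as" total seizures over total reported IVRS days, times 28.

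On what a call covers, Protocol 9.2.11 says only: "This IVRS telephone diary will be completed on a weekly basis during the OLE". Protocol 9.1.2.1 says that "patients/caregivers will be instructed to complete a weekly seizure reporting diary until the Follow-up visit using the IVRS". SAP 5.5.2 adds that calls are expected every 7 days. None of these says whether the caller reports since the last call or for the past 7 days.

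**The concern.** The on-time branch uses the plain date difference and the early branch uses the difference plus one. These are two conventions for one quantity, and the divisor stays at 7 when the gap goes from 6 days to 7. If the divisor does not equal the days over which seizures were counted, the rate is wrong by the ratio of the two.

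Percentage change in TSC-associated seizure frequency is a key secondary endpoint of the OLE. The same day count feeds OLE total, other and subtype seizures, the responder summaries and the LOCF tables. Under SAP 5.5.2.1, LOCF fills a withdrawn patient's later periods from the last 12 weeks of valid data, which can include an off-cycle final call. Protocol 13.2 says a cut of OLE data will support marketing applications.

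Early calls are foreseeable, since the SAP wrote a branch for them. As far as the table in Protocol Appendix 4 can be read, a call is due on the date of OLE end of treatment or withdrawal when study medication is tapered. Protocol 9.1.2.10 sets that visit at 364 days after B1 or "following early withdrawal from the study", and a withdrawal date need not fall on the weekly cycle.

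**Working it through.** **Inputs.** Gap g = current call date minus previous call date. From SAP 5.5.2, the divisor is d(g) = g + 1 for g < 7 and 7 for g ≥ 7, which is d(g) = min(7, g + 1).

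**The plan's own figure.** At g = 7 the plain difference gives 7, the SAP's value. An uncapped inclusive count would give 8. At g = 6 the plain difference gives 6, but the SAP gives 7.

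**Per-call error.** Ratio of SAP rate to true rate = days covered / d(g). Days covered are g if recall is since the last call, min(g, 7) if that is capped at 7 days, and 7 if recall is the past 7 days.

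| Gap g | SAP divisor | Since last call | Since last call, capped at 7 | Past 7 days |
|---|---|---|---|---|
| 1 | 2 | 0.50 | 0.50 | 3.50 |
| 2 | 3 | 0.67 | 0.67 | 2.33 |
| 3 | 4 | 0.75 | 0.75 | 1.75 |
| 4 | 5 | 0.80 | 0.80 | 1.40 |
| 5 | 6 | 0.83 | 0.83 | 1.17 |
| 6 | 7 | 0.86 | 0.86 | 1.00 |
| 7 | 7 | 1.00 | 1.00 | 1.00 |
| 10 | 7 | 1.43 | 1.00 | 1.00 |
| 14 | 7 | 2.00 | 1.00 | 1.00 |

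As a day-count check, fourteen calls at 6-day gaps span 14 × 6 = 84 days but receive 14 × 7 = 98 divisor days, and 84/98 = 0.86.

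**Average effect.** The documents give no call timings, so the mixes here are assumptions. Let a share p of calls be early, spread equally over gaps of 3, 4, 5 and 6 days, with the rest at 7 days. The mean of g/(g + 1) is 0.810 and the mean of 7/(g + 1) is 1.329. The average ratio is 1 − p + p × mean:

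- p = 0.1: 0.981 (since last call) or 1.033 (past 7 days).
- p = 0.3: 0.943 or 1.099.

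**One off-cycle withdrawal call.** Take a final call at a gap of 1 to 6 days, equally likely, after m weekly calls. The means over g = 1 to 6 are 0.735 and 1.858, and the period ratio is (m + mean)/(m + 1):

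| m | Since last call | Past 7 days |
|---|---|---|
| 1 | 0.867 | 1.429 |
| 3 | 0.934 | 1.215 |
| 11 | 0.978 | 1.071 |

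**Responder cut-off.** Suppose 2 of 12 calls come at 3-day gaps and the rest at 7.

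- Since last call: (10 + 2 × 0.75)/12 = 0.958. A true 48% reduction reads 1 − 0.52 × 0.958 = 50.2%.
- Past 7 days: (10 + 2 × 1.75)/12 = 1.125. A true 55% reduction reads 1 − 0.45 × 1.125 = 49.4%.

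**Unweighted averaging (secondary point).** With correct divisors, a constant rate and Poisson counts, averaging per-call rates costs precision only. For eleven 7-day calls and one 1-day call, the variance relative to pooling is [(11/7 + 1)/144] / (1/78) = 1.39.

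**The case against.** The strongest reply is that the IVRS script, which would settle the recall window, is not among the documents, and that the three branches together are an inclusive count capped at 7. The SAP counts inclusively elsewhere: day numbering (5.1.2), dosing days (5.6.1), and adverse event onset and resolution (5.6.2). For the first call, anchored on OLE Day 1, gap + 1 is indeed the number of OLE dates elapsed.

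The first-call case stands as a small exception. For every other call the rule is exact only if each report covers at most 7 calendar dates and includes both call dates. Neither document states such a window, and it would place the previous call's date in two reports.

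Other parts of the reply also stand:

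- The direction and overall size of the error are unknown. The early-call shares are assumed, and the responder examples were chosen to sit near 50%.
- The text of Appendix 4 is damaged, so it is thin evidence on how often early calls occur. A completer seen exactly 364 days after B1 is on cycle (364/7 = 52), although that visit has a ±7-day window.
- With eleven earlier weekly calls, one off-cycle call moves that patient's rate by only 2% or 7%, and the planned medians and quartiles would move little.
- If recall is since the last call without a cap, late calls err upwards and can offset early ones. Alternating 6- and 8-day gaps average to 1.00.

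**Conclusion.** The rule is wrong as written. The early-call divisor does not match the on-time one, and neither of the natural recall windows makes it right across gaps of 1 to 6 days. The label the SAP gives the divisor points to recall since the last call. On that reading early calls understate the seizure rate, which flatters the drug. If recall is the past 7 days, gaps of 1 to 5 days overstate it.

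Per call, the error runs from 14% to 50% too low, or from 17% too high to 3.5 times the true rate. Under the assumed mixes the average error is 1.9-5.7% too low or 3.3-9.9% too high. For one patient with an off-cycle withdrawal call after 1, 3 or 11 weekly calls, it is 13%, 7% or 2% too low, or 43%, 21% or 7% too high.

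Calls exactly 7 days apart carry no error. The late-call divisor is wrong only under uncapped recall since the last call. OLE efficacy is descriptive (Protocol 13.6.3), and the blinded primary and key secondary analyses and their Type I error control are untouched. The change should be made because the rule misstates an OLE key secondary endpoint and is easily corrected.

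**What to change.** State the OLE IVRS recall window in SAP 5.5.2 and use the days each call covers as the divisor:

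- since the last call: current date minus previous date, for every gap;
- since the last call, up to 7 days: min(gap, 7);
- past 7 days: 7 for every call.

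Define the start date for the first call. OLE Day 1 is expected to be the blinded end-of-treatment date (SAP 5.1.2), normally Day 113, which already lies in the blinded treatment period (SAP 5.1.3.4). It should not be counted in both phases.

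Compute each period's frequency as 28 × total seizures / total days covered, matching the blinded-phase formula. Under past-7-days recall, early calls overlap and the repeated days enter both numerator and denominator, so report how many calls overlap.

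The cost is one SAP paragraph and one derivation step. The existing rule already relies on the call dates, so no new data are needed.

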5.5.2.1 Sensitivity Analyses for the Primary Efficacy Endpoint

Blinded Phase:

The following sensitivity analyses will be conducted for the primary endpoint of the blinded phase:

- Primary endpoint analysis repeated using the PP analysis set.
- Wilcoxon rank-sum test on percentage change from baseline in TSC-associated seizure frequency during the treatment period. An estimate of the median differences between each GWP42003-P arm and placebo, together with approximate 95% CIs, will be calculated using the Hodges–Lehmann approach.
- A rank analysis of covariance (ANCOVA) on percentage change from baseline in TSC-associated seizure frequency during the treatment period.

The ranks of the percentage change from baseline and the baseline TSC-associated seizure frequency will be calculated. The rank of the percentage change from baseline will then be analyzed using an ANCOVA model with the rank of the baseline TSC-associated seizure frequency and stratified age group as covariates and treatment arm as a fixed factor. The estimated least squares means, treatment differences, together with the 95% CIs and p-values will be presented.

- ANCOVA of log transformed TSC-associated seizure frequency during the treatment period.

The TSC-associated seizure frequency during the treatment period and the baseline TSC-associated seizure frequency will be log transformed prior to analysis. The log transformed TSC-associated seizure frequency during the treatment period will then be analyzed using an ANCOVA model with the log transformed baseline TSC-associated seizure frequency and stratified age group as covariates and treatment arm as a fixed factor. The back transformed estimated treatment ratios, together with the 95% CIs and p-values will be presented.

If there are any patients with no TSC-associated seizures during the baseline or treatment periods, then 1 will be added to the TSC-associated seizure frequency for all patients prior to log transformation.

- ANCOVA on percentage change from baseline in TSC-associated seizure frequency during the treatment period including baseline and stratified age group as covariates

and treatment arm as a fixed factor. The estimated least squares means, treatment differences, together with the 95% CIs and p-values will be presented.

- Primary endpoint analysis repeated using the maintenance period (see Section 5.1.3.6) rather than the treatment period.

This analysis will include only patients who have at least 7 days of seizure data within the maintenance period.

- Primary endpoint analysis repeated using the titration period (see Section 5.1.3.5) each 4 weeks of the maintenance period (Week 1 to 4, Week 5 to 8 and Week 9 to 12 of the 12-week maintenance period).

These analyses will include only patients who have at least 7 days of seizure data within each corresponding 4 week period.

- Primary endpoint analysis repeated using the worst case of last observation carried forward (LOCF), next observation carried backward (NOCB) and the mean from the non-missing data for each patient (rounded up to the nearest integer) to impute missing data arising from unreported days in IVRS during the treatment period only (not the baseline period).

Any intermittent missing data for the number of TSC-associated seizures arising from unreported days in IVRS will be imputed using the worst (highest number of seizures) of the following for each patient: LOCF, NOCB and the mean daily number of seizures during the treatment period (rounded up to the nearest integer) based on using non-missing data:

$$\text{Number of seizures} \div \text{Number of reported days in IVRS}$$

- Primary endpoint analysis repeated using multiple imputation (MI) to impute data under the Missing Not at Random (MNAR) assumption (see Section 5.5.2.1.1).

Open-label Extension:

Open-label summaries will be repeated with the inclusion of an LOCF imputation step, which is described in the following steps:

- If a patient has valid data for ≥ 1 consecutive periods from and inclusive of the first period but only missing periods thereafter, then imputation of the missing period(s) will be carried out using the last 12 weeks of valid data (see Section 5.1.3.3).
- If a patient has intermittent missing periods (i.e. ≥ 1 missing period that falls after a populated period 1 and before subsequent populated periods), then the missing period(s) will be imputed with the closest earlier non-missing period of data.
- If the patient has ≥ 1 consecutive periods of missing data from and inclusive of the first period then no imputation will occur and data from the patient will be excluded from any LOCF presentations.

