#### 9.1.2 Open-label Extension

Patients who successfully complete the blinded phase will be invited to participate in the OLE when they reach the End of Treatment visit (Visit 10) of the blinded phase. They will be issued with the OLE patient information and informed assent or the patient/parent(s)/legal representative information and informed consent (as applicable). Following adequate time to discuss the study with the investigator, nurse, relatives or caregiver, patients/parent(s)/legal representatives who provide written informed consent/assent at Visit B1 will be enrolled into the OLE. The OLE period will last for a maximum of 1 year; however, patients in the US and Poland may have the opportunity to continue in the OLE beyond this.

On-label use of mTOR inhibitors (for the treatment of seizures or tumors) and general anesthesia are permitted in the OLE phase of the trial.

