#### 9.1.2.12 B12 (Day 389, Post-taper Safety Telephone Call)

A safety telephone call must be made two weeks  $(\pm 3 \text{ days})$  after the 'End of Taper Period' visit or date of final dosing. Patients or their caregivers will be asked for information on AEs, epilepsy-related hospitalizations, concomitant medications and/or changes to medication.

Following this call, the IVRS seizure reporting diary should be completed up to the Follow-up visit.

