5.1.3.3 Last 12 Weeks (OLE Only)

The last 12 weeks (84 days) of the OLE for IVRS based endpoints is defined as all available data from 12 weeks prior to the earliest of the date of the patient completing the OLE, or the last call to IVRS.

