5.1.4 Interim Analysis

No formal interim analysis is to be conducted in this trial. However, interim reporting of the OLE may be required to support regulatory filings. This SAP contains details for the final reporting of the double-blind and OLE phases of the trial. For interim reporting of the OLE,

the rules described in the SAP will be followed. However, only a subset of outputs including OLE data may be required to support regulatory filings.

If interim reporting of the OLE is required, then only data available up to and including the date of the data cut will be included. The below section describes how data will be selected for the interim reporting.

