The assumptions of normality and homogeneity of variance, for endpoints analyzed using parametric tests, will be checked where appropriate via examination of residual plots as well as computation of summary statistics for normality using the Shapiro-Wilk statistical test. If assumptions are violated then alternative non-parametric techniques will be used. In this instance the original parametric tests will be presented as a sensitivity analysis.

Open-label Extension:

All endpoints will be summarized on the OLE safety analysis set, unless specified otherwise.

Endpoints will be summarized by treatment received during the double-blind phase (GWP42003-P or Placebo, i.e. not split by dose) and overall.

For seizure endpoints, the OLE treatment phase will be split into 12 week periods, for example:

- OLE Week 1 (OLE Day 1) to OLE Week 12 (Day 84)
- OLE Week 13 (OLE Day 85) to OLE Week 24 (OLE Day 168)
- OLE Week 25 (OLE Day 169) to OLE Week 36 (OLE Day 252)
- OLE Week 37 (OLE Day 253) to OLE Week 48 (OLE Day 336)
- OLE Week 49 (OLE Day 337) to OLE Week 60 (OLE Day 420)
- Etc.

In addition, seizure data will be presented for the full OLE treatment phase as well as the last 12 weeks of the OLE treatment phase (see Section 5.1.3.3).

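### The open-label LOCF rule copies early seizure results into 12-week periods that a patient had not reached at a data cut or was never scheduled to have

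*SAP*

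**What the plan says.** SAP 5.5.2.1 (Open-label Extension): "Open-label summaries will be repeated with the inclusion of an LOCF imputation step". A patient with data from the first period onward and nothing after some point has every later period filled: "imputation of the missing period(s) will be carried out using the last 12 weeks of valid data". No withdrawal condition is attached, and neither the data cut nor the planned length of the OLE limits the fill.

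SAP 5.5.1 divides the OLE into 12-week periods, gives five examples ending with Weeks 49–60 (Days 337–420), and adds that the list continues.

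Protocol 9.1.2 limits the OLE to one year, except that "patients in the US and Poland may have the opportunity to continue in the OLE beyond this".

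Protocol 13.2 plans a cut of OLE data to support marketing applications. SAP 5.1.4 says that for interim OLE reporting "the rules described in the SAP will be followed", using only data up to the cut.

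Two places describe the carried window. SAP 5.1.3.3 takes the data from "12 weeks prior to the earliest of the date of the patient completing the OLE, or the last call to IVRS". SAP 5.5.1, citing that section, describes the same summary with the words "as well as the last 12 weeks of the OLE treatment phase".

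The protocol schedules seizure calls after treatment ends. Section 9.1.2.12 says: "Following this call, the IVRS seizure reporting diary should be completed up to the Follow-up visit". Section 9.1.2.1 asks for weekly calls until Follow-up. Section 9.1.2.11 and Appendix 4 ask for only one more call after dosing ends.

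**The concern.** A blank period can arise in three ways: the patient withdrew, the patient is still in the OLE but has not got that far, or the period lies beyond the planned OLE. Carrying a value forward is a check on drop-out only in the first case. In the other two it enters an early result under a later-period label.

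The outputs concerned are the LOCF repeats, for example OLE Tables 9.1.1.2, 9.1.2.2 and 9.3.1.2 and OLE Figures 9.1.2 and 9.2.2. They bear on the long-term seizure effect, which is an OLE secondary objective. If copies from continuing patients are mixed with copies from withdrawals, a flat curve cannot be read as maintained effect. SAP 5.5.3.1.1 also allows withdrawn patients to count as OLE responders, so an early responder status can be carried to late periods. For a patient with 12 weeks of data, the carried window includes the two-week transition and the three-week titration, 5 of its 12 weeks.

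The second issue is the end of the window. A withdrawn patient has no OLE completion date, so the definition in SAP 5.1.3.3 falls back on the last call, which the protocol can place after the last dose. The same definition serves the stand-alone last-12-weeks summary.

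**Working it through.** **Period boundaries.** Period k runs from Day 84(k − 1) + 1 to Day 84k. For k = 5 this gives 84 × 4 + 1 = 337 and 84 × 5 = 420, which reproduces the SAP's Weeks 49–60.

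**Scheduled days for a one-year patient.** OLE treatment ends at Visit B10, Day 365 (Protocol 9.1.2.10).
- Periods 1–4 end at Day 336 and lie wholly inside the schedule.
- Period 5 contains 365 − 337 + 1 = 29 scheduled days, so a completer normally has data there.
- Period 6 (Weeks 61–72) starts at Day 421. It contains no treatment days and begins after the scheduled Follow-up at Day 403. The rule fills it and every later period.

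**Copies at a data cut.** A continuing patient with w weeks of data has w/12 periods populated, so 4 − w/12 of the first four are copied: 3 for w = 12, 2 for w = 24, 1 for w = 36.

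**Share of patients (assumption).** The documents give no OLE entry dates or cut date. Assume uniform entry over 52 weeks and ignore withdrawals. Patients with under 36 weeks of follow-up have no data in Weeks 37–48.
- Cut 52 weeks after first entry: entry after week 52 − 36 = 16, so (52 − 16)/52 = 36/52 = 69%.
- Cut at 78 weeks: entry after week 78 − 36 = 42, so (52 − 42)/52 = 10/52 = 19%.

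**Off-drug share of the carried value, withdrawn patient.** SAP 5.5.2 averages rates over calls and counts any gap longer than 7 days as 7, so the relevant unit is the call. Day 0 is end of treatment, with weekly calls before it.
- Appendix 4, tapered: last call at +37, window −46 to +37. This holds 7 on-drug calls (0 to −42), 1 taper call (+7) and 1 off-drug call, so 1/9 = 11%.
- Appendix 4, not tapered: last call at +27, window −56 to +27. This holds 9 on-drug calls and 1 off-drug call, so 1/10 = 10% (1/9 if no call is made on Day 0).
- Weekly calls to Follow-up: 4 off-drug calls of 12, so 33%, tapered or not.

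**Completers.** If completion means Visit B10, the window is Days 365 − 84 + 1 = 282 to 365, all on drug.

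**Direction (assumed rates).** Take an on-drug rate of 0.5 times baseline (−50%) under the tapered Appendix 4 schedule.
- Off-drug rate 0.5: the carried change is −50.0%.
- Off-drug rate 1.0: 8/9 × 0.5 + 1/9 × 1.0 = 0.556, so −44.4%.
- Off-drug rate 1.5: 8/9 × 0.5 + 1/9 × 1.5 = 0.611, so −38.9%.

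If seizures rise off drug, the carried value looks worse, not better.

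**The case against.** LOCF is a repeat analysis under a sensitivity heading. The observed-period tables stay (OLE Tables 9.1.1.1, 9.1.2.1, 9.3.1.1), and further tables and figures are restricted to patients with observed Week 37–48 data (OLE Tables 9.1.1.3, 9.1.2.3, 9.3.1.3 and 9.3.2.3; OLE Figures 9.1.3 and 9.2.3). OLE efficacy is descriptive, and the OLE primary endpoint is safety. SAP 5.1.4 says that only a subset of outputs may be produced at an interim, and nothing confirms that the LOCF tables would be among them. The period list is illustrative, and the continuation rules for the US and Poland sit in annexes outside these documents. SAP 5.5.1 refers to the treatment phase, so off-drug data may never have been intended.

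Much of this stands, and it limits the point to the LOCF outputs and the last-12-weeks window. It does not remove the point. The observed by-period tables include only patients still contributing data, so LOCF is the planned by-period check on drop-out, and the written rule cannot separate drop-out from incomplete follow-up. A programmer following SAP 5.5.2.1 literally would fill those cells. The treatment-phase wording in 5.5.1 makes the window an unresolved inconsistency rather than an instruction to use off-drug data, since the section it cites does not contain that limit.

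**Conclusion.** The point holds for the OLE LOCF outputs. As written, the rule fills periods not reached at a cut (3, 2 or 1 of the first four for patients with 12, 24 or 36 weeks) and unscheduled periods from Week 61 for one-year patients. That follows from the text. The 69% and 19% do not: they rest on assumed accrual and cut dates and only illustrate how far the result can vary. The window issue is smaller, about 1 call in 9 or 10 under Appendix 4 and 4 in 12 under weekly calls to Follow-up. It concerns withdrawn patients, and completers only if completion is read as a date after treatment ends.

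Three stronger readings are tempting but not supported:
- A reader might infer that the long-term efficacy summaries as a whole fail to show long-term effect. The observed-data outputs are not touched by this rule.
- A reader might count calendar days and put 37/84 = 44% (tapered) or 27/84 = 32% (not tapered) of the carried value after treatment. The rate is averaged over calls, and 10 of the 37 days are taper, when the patient is still dosed.
- A reader might think that Weeks 49–60 are filled for every one-year completer. Days 337–365 fall in that period.

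Nothing here affects the blinded-phase analyses, their error control or the sample size.

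**What to change.** In SAP 5.5.2.1 (Open-label Extension), impute only for patients who withdrew from the OLE, and only for periods they would have completed by the data cut and by the planned, country-specific OLE end. Leave all other periods missing. Report observed and imputed n for each period. For a one-year patient, Weeks 49–60 run past Day 365, so this wording leaves them unimputed after withdrawal; the SAP should say so.

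In SAP 5.1.3.3, end the window at the earliest of the End of Treatment/Withdrawal visit, the last pre-taper dose, the data cut or the last IVRS call, so that it agrees with SAP 5.5.1. The post-treatment call instructions in Protocol 9.1.2.1, 9.1.2.11, 9.1.2.12 and Appendix 4 should also be reconciled.

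The cost is two SAP sentences, a revised imputation flag and two extra counts per period. The LOCF tables will show smaller n in late periods.
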